6. STUDY PROCEDURES

6.1 Schedule of Evaluations

Randomized Control Trial

Treatment Variables. Main patient reported treatment outcomes (PROs) include pain intensity and anxiety. The use of self-reported pain ratings to assess pain is standard clinical practice.^{68,69} Although self-report of pain intensity is subjective, a reliable physiological measure to quantify pain has not been identified.⁷⁰ These measures will be collected via tablet computer in the PHI-approved data collection tool (REDCap). A similar process was used in [name]'s pilot RCT. The study staff will hand the patient a tablet for confidential self-administration. Once the patient completes the questionnaires, the answers will be masked so the research staff will not have access to the scores. To keep research staff blinded to scores, the data collection tool will be designed so that the study staff will only be able to determine that valid pain and anxiety scores were entered by the patient. In other words, staff will not have access to the actual pain or anxiety scores until the statistician conducts the final analysis. Data will be collected as shown in Table below.

Treatment Variables	Measure/Source	Data Collection Time point			
		Pre-Treatment	Post-Treatment	ED Discharge	1-week and 4-week Follow-up
Primary Assessment (* and bold)					
Pain Intensity	Numeric Rating Scale, 0-10^{58,59}	X	X*	X*	X^
Anxiety	Numeric Rating Scale, 0-10^{58,59}	X	X*	X*	X^
Secondary Assessment (^ and italic)					
All pain medications in the ED	EHR			X^	
Pain medication/opioid use	Self-report				X^
Baseline variables of interest					
Demographics	EHR data and self-report	X			
Current Medications		X			
Opioid use – last 30 days	Self-report	X			
Previous acupuncture use		X			

ED visits in last year	X
Other variables of interest	
Expectancy	Self-report
Satisfaction questions	X
ED impact (ACUPUNCTURE ONLY)	X

Qualitative Interviews

Patient Interview Guide

U01 Acupuncture Study Patient Interview Topic Guide Preliminary Draft 10-23-20
1. Pain narrative—history, cause, impact, course, treatment experiences Possible prompts: i. Tell me about your pain condition... ii. How long have you had it? iii. What causes it? iv. How does it impact you? v. Tell me about your pain condition over time—wax/wane? Always the same? Exacerbating issues? vi. Tell me about your treatment and management experiences

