1 week follow-up Assessment (Follow-up) will be obtained via REDCap based text message or email (or phone call from research staff) at 1 week (+/- 4 days) of patient's ED discharge for both arms. To maintain assessor blinding, any 1-week phone calls (if needed) will be conducted by a research staff (SC or RA) who did not interact with the patient during their study participation in the ED.

- Pain Assessment (Post) using a 0-10 NRS
- Anxiety scores using a 0-10 NRS
- Satisfaction and will be measured through brief questions. All participants will be asked to answer;
 - “How satisfied are you with how your pain was managed during your ED visit” on the 5-point Likert scale.
 - “Overall how satisfied are you with your treatment during your ED visit?” on the same Likert Scale.
- Pain medications utilized from ED discharge to 1 week after discharge will be obtained from patients via phone call, email, or text messaging via the secure REDCap electronic data collection tool.

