2. Please rate your anxiety, **right now**, on a scale of 0 to 10, where 0 is no anxiety, and 10 is the worst anxiety imaginable.

0 1 2 3 4 5 6 7 8 9 10

SECTION 3 – Satisfaction

3. How satisfied are you with how your pain was managed during your ED visit?

- a. Very Unsatisfied
- b. Somewhat Unsatisfied
- c. Neutral
- d. Somewhat Satisfied
- e. Very Satisfied

4. Overall how satisfied are you with your treatment during your ED visit?

- a. Very Unsatisfied
- b. Somewhat Unsatisfied
- c. Neutral
- d. Somewhat Satisfied
- e. Very Satisfied

FOLLOW UP FORM for 1 week F/U AND 4 week F/U – To be completed by everyone, ideally from an automatic text and email generated by REDCap. If not by email, coordinator will text or phone the participant and enter the answers into REDCap.

Instructions: Below are some questions that ask you to remember what happened since your discharge from the Emergency Room on [er_visit_date].

Section 1-Medications

1. Since your discharge from the Emergency Room on [er_visit_date], have you taken any pain medications for your medical condition?
 - a. Yes
 - b. No
 - c. I don't know
 - i. If yes, “were these medications prescribed by a medical professional?

Check all that apply:

1. Yes, by Emergency room provider

2. Yes, by Primary Care Provider
 3. Yes, by Other medical professional [FREE TEXT]
 4. No
 5. I don't know
2. [branched from 1.a.i.1] Since your discharge, which pain medication(s) was prescribed by your EMERGENCY ROOM PROVIDER? Please select all that apply. (radio):
 1. Oxycodone (OxyContin, Oxecta, Roxicodone)
 2. Oxycodone / Acetaminophen (Percocet, Endocet, Roxicet)
 3. Oxycodone and Naloxone (Targiniq ER)
 4. Fentanyl (Actiq, Duragesic, Fentora)
 5. Methadone (Dolophine, Methadose)
 6. Morphine (Astramorph, Avinza, Kadian, MS Contin, Ora-Morth SR)
 7. Codeine
 8. Tylenol with codeine
 9. Hydrocodone (Hysingla ER, Zohydro ER)
 10. Hydrocodone / Acetaminophen (Lorcet, Lortab, Norco, Vicodin)
 11. Hydromorphone (Dilaudid, Exalgo)
 12. Aspirin
 13. Tylenol
 14. Ibuprofen
 15. Naproxen
 16. Celebrex
 17. Other: [FREE TEXT]
 18. Do not know
 19. Decline to answer
- a. How often have you taken these pain medication(s) on average?
 1. Several times a day
 2. Once a day
 3. Several times a week
 4. Once a week
 5. Several times per month
 6. Once per month
 7. Can't recall
 8. Decline to answer
 9. Other: [FREE TEXT]

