3. [branched from 1.a.i.2] Since your discharge, which pain medication(s) was prescribed by your PRIMARY CARE PROVIDER? Please select all that apply. (radio):
 1. Oxycodone (OxyContin, Oxecta, Roxicodone)
 2. Oxycodone / Acetaminophen (Percocet, Endocet, Roxicet)
 3. Oxycodone and Naloxone (Targiniq ER)

4. Fentanyl (Actiq, Duragesic, Fentora)
5. Methadone (Dolophine, Methadose)
6. Morphine (Astramorph, Avinza, Kadian, MS Contin, Ora-Morth SR)
7. Codeine
8. Tylenol with codeine
9. Hydrocodone (Hysingla ER, Zohydro ER)
10. Hydrocodone / Acetaminophen (Lorcet, Lortab, Norco, Vicodin)
11. Hydromorphone (Dilaudid, Exalgo)
12. Aspirin
13. Tylenol
14. Ibuprofen
15. Naproxen
16. Celebrex
17. Other: [FREE TEXT]
18. Do not know
19. Decline to answer

- a. How often have you taken these pain medication(s) on average?
 1. Several times a day
 2. Once a day
 3. Several times a week
 4. Once a week
 5. Several times per month
 6. Once per month
 7. Can't recall
 8. Decline to answer
 9. Other: [FREE TEXT]
4. [branched from 1.a.i.3] Since your discharge, which pain medication(s) was prescribed by ANOTHER MEDICAL PROFESSIONAL? Please select all that apply. (radio)
 1. Oxycodone (OxyContin, Oxecta, Roxicodone)
 2. Oxycodone / Acetaminophen (Percocet, Endocet, Roxicet)
 3. Oxycodone and Naloxone (Targiniq ER)
 4. Fentanyl (Actiq, Duragesic, Fentora)
 5. Methadone (Dolophine, Methadose)
 6. Morphine (Astramorph, Avinza, Kadian, MS Contin, Ora-Morth SR)
 7. Codeine
 8. Tylenol with codeine
 9. Hydrocodone (Hysingla ER, Zohydro ER)
 10. Hydrocodone / Acetaminophen (Lorcet, Lortab, Norco, Vicodin)
 11. Hydromorphone (Dilaudid, Exalgo)

12. Aspirin
13. Tylenol
14. Ibuprofen
15. Naproxen
16. Celebrex
17. Other: [FREE TEXT]
18. Do not know
19. Decline to answer

a. How often have you taken these pain medication(s) on average?

1. Several times a day
2. Once a day
3. Several times a week
4. Once a week
5. Several times per month
6. Once per month
7. Can't recall
8. Decline to answer
9. Other: [FREE TEXT]

5. [branched from 1.a.i.4] Since your discharge from the emergency room on [er_visit_date], which pain medication(s) have you taken (not prescribed by your emergency room provider, primary care provider or other medical professional)? Please select all that apply

1. Oxycodone (OxyContin, Oxecta, Roxicodone)
2. Oxycodone / Acetaminophen (Percocet, Endocet, Roxicet)
3. Oxycodone and Naloxone (Targiniq ER)
4. Fentanyl (Actiq, Duragesic, Fentora)
5. Methadone (Dolophine, Methadose)

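### Follow-up form: the list of non-prescribed pain drugs opens only from a bare 'No', so some patients who use both prescribed and non-prescribed drugs may never see it

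*Combined protocol and SAP*

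**What the plan says.** The Schedule of Evaluations (section 6.1) marks "Pain medication/opioid use", by self-report at the 1-week and 4-week follow-ups, as a secondary assessment. Section 6.2.4 adds: "Pain medications utilized from ED discharge to 1 week after discharge will be obtained from patients via phone call, email, or text messaging"; section 6.2.5 does the same for 4 weeks.

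The instrument is the Follow Up Form in Appendix B. Item 1 asks whether any pain medication has been taken since discharge. If so, item 1.a.i asks "were these medications prescribed by a medical professional", under the instruction "Check all that apply". There are three prescribed sources (the first is "Yes, by Emergency room provider", then primary care and another professional), a plain 'No', and 'I don't know'.

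Each drug list is tied to one option. Item 2 reads "branched from 1.a.i.1] Since your discharge, which pain medication(s) was prescribed by your EMERGENCY ROOM PROVIDER"; items 3 and 4 do the same for the other two prescribers. Item 5 reads "branched from 1.a.i.4] Since your discharge from the emergency room on [er_visit_date], which pain medication(s) have you taken (not prescribed by your emergency room provider". No item branches from 'I don't know', and no rule makes 'No' exclusive of the 'Yes' options.

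**The concern.** The question treats all of a patient's pain drugs as one group. Consider a patient taking a drug prescribed in the ED plus ibuprofen bought at a pharmacy. To reach item 5 that patient must answer both 'Yes' and 'No' to the same question. The instruction allows it, but the label does not say that 'No' can mean that some of the drugs were not prescribed. A patient who ticks only the 'Yes' source is never shown item 5, and the record may then look like no non-prescribed use.

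Three features of the plan make this worth attention:

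- Section 10.2 has the electronic health record supplying ED pain medication and opioid prescriptions at discharge. Nothing there covers non-prescribed use afterwards, so self-report is the only planned source. Item 5 lists opioids as well as over-the-counter drugs.
- An item that branching never opened need not show up as missing in the completeness review of sections 9.5.1 and 9.6.
- The preferred route is an automatic text or email, with nobody present to explain the question.

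If acupuncture changes how often patients leave with a prescription, the share of patients exposed to this risk differs by arm, and so would any under-count.

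**Working it through.** The plan states no figure on this point, so there is none to reproduce. The check has two parts.

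**1. What the printed branching does, for a patient who took a pain drug**

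| Ticked at 1.a.i | Lists shown | Non-prescribed use |
|---|---|---|
| 'No' only | item 5 | asked |
| a 'Yes' source and 'No' | item 2, 3 or 4, and item 5 | asked |
| 'Yes' source(s) only | item 2, 3 or 4 | not asked; might be entered under a prescriber |
| 'I don't know' only | none | not asked |

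The exposure lies in the last two rows. The third row depends on how many mixed users leave 'No' unticked.

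**2. What that could do to recorded use (illustration only)**

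The inputs are assumptions; the documents give none of them.

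- u: true non-prescribed use, the same in both arms; 40% or 60%.
- p: proportion holding a prescription, independent of non-prescribed use; 30% acupuncture and 50% usual care, or 40% in both.
- q: share of mixed users who do not also tick 'No'; 0 to 1.

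Recorded use in an arm = u × (1 − p × q).
Under-count in an arm = u × p × q.
Spurious arm difference = u × q × (difference in p).

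Example with u = 0.6, q = 0.5:

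- acupuncture: 0.6 × (1 − 0.3 × 0.5) = 0.51
- usual care: 0.6 × (1 − 0.5 × 0.5) = 0.45
- under-counts: 9 and 15 points; spurious difference 0.6 × 0.5 × 0.2 = 0.06, or 6 points

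With prescribing of 30% versus 50%:

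| q | u = 60%: recorded | Difference | u = 40%: recorded | Difference |
|---|---|---|---|---|
| 0 | 60% vs 60% | 0 | 40% vs 40% | 0 |
| 0.25 | 55.5% vs 52.5% | 3 points | 37% vs 35% | 2 points |
| 0.5 | 51% vs 45% | 6 points | 34% vs 30% | 4 points |
| 1 | 42% vs 30% | 12 points | 28% vs 20% | 8 points |

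With prescribing of 40% in both arms, the spurious difference is 0 at every q, while the under-count remains. At u = 60% and q = 0.5, both arms record 0.6 × (1 − 0.4 × 0.5) = 48%.

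The model treats every non-prescribed drug of a mixed user who skips 'No' as lost. Any that are entered under items 2 to 4 would be misattributed instead, which makes the loss smaller than shown.

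**The case against.** A reader might infer that the form drops the non-prescribed drugs of every patient who also has a prescription. The documents do not support that. Item 1.a.i is multi-select, each list opens from its own option, and nothing closes item 5 when a 'Yes' is also ticked. Complete loss corresponds to q = 1, which the form does not impose. A reader might also take a figure from the table as the expected bias. That is not supported either: prescribing by arm, rates of mixed use and the response to the label are all absent from the documents.

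Other mitigating points are fair:

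- Aspirin, Tylenol, ibuprofen and naproxen also appear in the lists under items 2 to 4. Some over-the-counter use may be entered there, under the wrong source but not lost from total exposure.
- When the follow-up is done by phone, the caller can clarify.
- ED opioid prescribing comes from the health record and does not depend on this item.
- This is a feasibility trial with recruitment and retention as its primary outcomes. Section 9.5 plans descriptive summaries, and no between-arm test of post-discharge medication use is specified.

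These points limit the weight of the issue. They do not remove the wording problem: the label still invites a mixed user to skip the only option that opens item 5, and none of the mitigations fully recovers non-prescribed use. The protocol's own primary objective is to refine procedures for a later, fully powered trial, and section 2.1 names opioid use at follow-up as a gap left by earlier trials. A weak item in this form is therefore worth correcting now.

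**Conclusion.** The form can record both kinds of drug, but it opens the non-prescribed list only from an option that reads as excluding the others. Some mixed users, and any patient who ticks only 'I don't know', may never be asked about non-prescribed drugs. The branching is certain from Appendix B; how patients respond to it is a judgement about wording.

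The size is unknown. It is zero if all mixed users tick both options. Under the assumed rates above, the spurious arm difference is 0 to 12 points, and it requires both a prescribing gap between arms and omission of 'No'. With equal prescribing only an under-count remains. This is a modest data-quality point on a listed secondary assessment, and it does not affect the primary outcomes.

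**What to change.** Make one of two changes to the follow-up form:

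- Relabel option 4 of item 1.a.i as 'Some or all were not prescribed (over the counter or other)', so that it sits naturally beside a 'Yes' source; or
- Show item 5 to everyone who answers 'Yes' to item 1, opened by a yes/no question on whether any pain medicine not prescribed for them was also taken, followed by the existing drug list. This route also reaches patients who tick only 'I don't know'.

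For data already collected, flag as 'non-prescribed use possibly not asked' only those records with 'Yes' at item 1 in which 'No' was not ticked at 1.a.i. Records with 'No' ticked, alone or with a 'Yes' source, did open item 5 and should stand.

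The cost is a label change, or one branching change and one extra question, plus a derived flag. Treatment and sample size are untouched.

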6.2.5 Completion/Final Evaluation

Four Week Follow-Up Assessment Visit

4 week follow-up Assessment (Follow-up) will be obtained via REDCap based text message or email (or phone call from research staff) at 4 week (+/- 4 days) of patient's ED discharge for both arms. To maintain assessor blinding, any 4-week phone calls (if needed) will be conducted by a research staff (SC or RA) who did not interact with the patient during their study participation in the ED.

- Pain Assessment (Post) using a 0-10 NRS
- Anxiety scores using a 0-10 NRS
- Satisfaction and will be measured through brief questions. All participants will be asked to

answer:

- "How satisfied are you with how your pain was managed during your ED visit" on the 5-point Likert scale.
- "Overall how satisfied are you with your treatment during your ED visit?" on the same Likert Scale.
- Pain medications utilized from ED Discharge to 4 weeks after discharge will be obtained from patients via phone call, email, or text messaging via the secure REDCap electronic data collection tool.

Early Termination

The study doctor or the sponsor can stop a subject's participation at any time without their consent for the following reasons:

- If it appears to be medically harmful to them;
- If they fail to follow directions for participating in the study;
- If it is discovered that they do not meet the study requirements;
- If the study is canceled; or
- For administrative reasons, including competitive enrollment (e.g. the target number of subjects has entered the study.)
- If the patient's clinical condition worsens emergently as determined by the ED physician/clinician.

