10.2 Data Management

In our pilot RCT, we developed and successfully used a basic electronic data collection tool (StudyTRAX). In Year 1, we will build a comprehensive study management database and data collection platform using REDCap and confirm the ability to blind assessors to patient scores and text message subjects for the 1-week follow-up assessment. Our team has successfully used REDCap for multisite data collection in the BraveNet PBRN as well as across [name] multi-clinic studies.

Informed consents and HIPAA authorizations will be collected as hard copy paper documents; these will be kept by the study team in individual patient binders in locked filing cabinets of a secure, badge-access location at each site.

Demographic and baseline data will be collected both by the SC and through EHR data extraction at baseline. The data collected by research staff will be entered directly into an electronic data collection tool. There will be no hard copies of this data.

Patient Reported Outcomes (PROs) (pain intensity and anxiety) will be collected by study staff (SC or RA), rather than by the acupuncturists delivering treatments. All PROs will be entered directly by the study participant on a tablet via REDCap and will disappear from view once entered so neither the participant nor research staff will have access to the scores. The scores will then be exported to a password protected database. There will be no hard copies of this data.

Satisfaction data will be collected as part of ED-discharge and at 1-week and 4-week follow up for patients. ED staff will complete a one-time brief survey at the end of the enrollment period.

EHR data will be electronically extracted by each site with HIPAA protected identifiers as limited datasets. The data extracted from EHR will be verified by MRN and date with our electronic platforms. EHR extracted data will include demographic data, pain medication use in the ED, and opioid prescriptions at discharge. Both [name] and [name] have extensive experience in use of EHR data. There will be no hard copies of this data.

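### Follow-up medication items 2–4 ask what was prescribed rather than what was taken, so a patient who took one prescribed drug but left an opioid from the same prescriber untaken can be recorded as an opioid user

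*Combined protocol and SAP*

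**What the plan says.** Section 6.1 (Schedule of Evaluations) lists "Pain medication/opioid use" by self-report as a secondary assessment at the 1-week and 4-week follow-ups. Sections 6.2.4 and 6.2.5 describe the same variable in terms of use: "Pain medications utilized from ED discharge to 1 week after discharge will be obtained from patients" and "Pain medications utilized from ED Discharge to 4 weeks after discharge will be obtained from".

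The instrument is the follow-up form in Appendix B, Section 1 (Medications):

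- Item 1 asks "have you taken any pain medications for your medical condition". Only a Yes goes further.
- Item 1.a.i asks who prescribed these medications. Each ticked source opens its own item.
- Item 2 (emergency room): "Since your discharge, which pain medication(s) was prescribed by your EMERGENCY ROOM PROVIDER".
- Item 3 (primary care): "Since your discharge, which pain medication(s) was prescribed by your PRIMARY CARE PROVIDER". Item 4 does the same for another medical professional.
- Item 5 (non-prescribed): "which pain medication(s) have you taken (not prescribed by your emergency room provider, primary care provider or other medical professional".
- Each of items 2–5 is followed by one question on average frequency, answered once for all ticked drugs. The scale runs from several times a day down to once per month, plus can't recall, decline and free-text other.

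Items 2–4 invite the patient to choose every drug that applies, yet carry a radio-button marking.

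Prescribing has its own source in section 10.2: "EHR extracted data will include demographic data, pain medication use in the ED, and opioid prescriptions at discharge". No section gives a rule for deriving opioid use from items 1–5.

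**The concern.** The protocol wants use, and the form asks for prescriptions where most prescribed opioids would be recorded. The form itself draws the distinction, because item 5 asks about taking. Since ED discharge opioid prescribing comes from the EHR, the self-report adds information mainly if it measures use.

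Section 2.1 counts the lack of follow-up opioid data in earlier ED trials among the gaps this study will fill. The primary objective (section 1.1) is to refine procedures for a fully powered trial, so a form that passes the completeness checks of section 9.5.1 while recording the wrong construct could be carried forward. If acupuncture led some patients to take a prescribed non-opioid and leave the opioid untouched, these items could blur that difference.

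**Working it through.** No formula applies. The check is to follow each type of patient through the branching (item 1, item 1.a.i, items 2–5, frequency), assuming that each question is answered as worded and that items 2–4 accept several answers.

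| Patient since discharge | Path through the form | Recorded as opioid user? |
|---|---|---|
| (a) Prescribed an opioid, took no pain medication | Item 1 = No; items 2–4 never open | No (correct) |
| (b) Prescribed an opioid, took only non-prescribed non-opioids | 1.a.i refers to drugs taken; only item 5 opens | No (correct) |
| (c) Took a non-opioid from one source; was also prescribed an opioid by that source and did not take it | That source's item opens and asks what was prescribed; both drugs are ticked | Yes, if the variable is derived from ticked drugs (wrong) |
| (d) Took the prescribed opioid | That source's item opens; opioid ticked | Yes (correct) |

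If the untaken opioid in (c) came from a different source than the drug taken, that source is not ticked at 1.a.i and its item does not open. The misclassification is therefore limited to one prescriber, several drugs, opioid left untaken.

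**Can anything else on the form correct type (c)?** The frequency sub-item does ask about taking, but one answer serves all ticked drugs and there is no zero category. The ibuprofen frequency of a type (c) patient attaches to the opioid as well. Only the free-text option could record non-use, and nothing prompts for it.

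**Can the EHR correct it?** No. For type (c) the EHR shows an opioid prescription and item 2 repeats it. Both are prescribing data. The EHR does help with types (a) and (b): an ED discharge opioid together with item 1 = No, or with only item 5 opened and that opioid not ticked, points to an unused prescription.

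**What if the items are built as single-choice?** A type (c) patient can then record one drug only. Choosing the opioid is a false positive; choosing the other drug happens to classify opioid use correctly. A patient who took both and chooses the non-opioid becomes a false negative. The direction of the error is then unknown.

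**How many patients?** This would need the share discharged with an opioid and another drug from one source, the share of those taking only the other drug, the share reached at follow-up, and the share who tick the untaken drug. The documents give none of these for this trial.

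**The case against.** The strongest reply is that the items are better than they look in isolation. Item 2 comes after two questions about drugs taken and is followed by one about how often they were taken, so many patients may read it as asking which of their taken drugs came from the emergency room. That is plausible and means type (c) patients *can* be miscounted, not that they always are. It does not remove the problem: an analyst seeing a ticked opioid cannot tell which reading the patient used.

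A reader might infer three stronger things that the documents do not support:

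- *That the outcome counts patients generally who never took their opioid.* Items 1 and 1.a.i exclude those who took nothing or only non-prescribed drugs.
- *That the study could not detect opioids left unused.* Section 10.2 supplies discharge opioid prescriptions, and combining them with item 1 reveals some of these cases. Use is also recoverable for patients with one drug per prescriber.
- *A headcount.* Suppose 10–30% leave with both drugs and 20–40% of those take only the non-opioid. Then 0.10 × 0.20 = 2% and 0.30 × 0.40 = 12%, or 3 to 18 of 150. Those inputs are pure assumption, and the product also supposes full follow-up and that every such patient ticks the unused opioid. At the pilot RCT's roughly 35% 30-day follow-up (section 2.2), the same assumptions give 0.35 × 3 ≈ 1 to 0.35 × 18 ≈ 6. I rely on neither range.

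It is also fair that this is a secondary assessment. Section 9.5 plans descriptive summaries of secondary outcomes, and sections 9.5.1 and 9.5.2 do not name opioid use among the outcomes they set out.

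**Conclusion.** The mismatch stands in a limited form. Items 2–4 record prescribing where the protocol specifies use. For a patient who took one drug and left untaken an opioid from the same source, the structured data cannot separate non-use from use. The trace assumes that items are answered as worded and that opioid use is derived from ticked drugs; no derivation rule is stated. The number affected cannot be computed from the documents, and the radio marking leaves even the direction of error open if the items are single-choice. No sample size, power or error rate changes, and no recruitment or retention conclusion depends on it. It is a cheap improvement, worth making because the trial exists to refine its procedures.

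**What to change.** 1. Reword items 2–4 to match item 5: *Which of the pain medication(s) prescribed by your [source] have you taken since your discharge?*
2. Build them as multi-select, remove the radio marking, and add *None of these taken*.
3. Ask frequency for each ticked drug, or at least separately for opioids. Rewording the stems alone would leave opioid frequency unknown for anyone taking two drugs.
4. State the derivation: opioid use comes only from the taken responses (items 2–5), and ED discharge opioid prescribing comes from the EHR extract.

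For data already collected with multi-select items, report opioid use as a range. The upper count is every patient with a ticked opioid. The lower count is those with an opioid ticked in item 5, or with only opioids ticked under some source in items 2–4; since 1.a.i says something from that source was taken, these patients took one.

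The cost is a small REDCap change, review of the modified form under section 11.1, and slightly more burden for patients taking several drugs.
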